### **3.8. Subpopulations**

Subgroup analyses using pooled data for the primary and secondary efficacy endpoints as well as TEAE incidences are planned as follow:

- By age (age categories <65 and ≥ 65 years old)
- By gender

### **3.9. Withdrawals, Dropouts, Loss to Follow-up**

Patients must be withdrawn from the study for any of the following, but not limited to:

- Withdrawal of consent.
- The patient is unwilling or unable to comply with the protocol.
- The patient meets any of the Exclusion Criteria after enrolling in the study that in the opinion of the Investigator represents a safety risk to the patient.

All efforts will be made to complete and report the observations as thoroughly as possible up to the date of withdrawal. All information, including the reason for withdrawal from study, must be recorded in the eCRF.

Any patient who withdraws consent to participate in the study will be removed from further treatment and study observation immediately upon the date of request. These patients should be encouraged to complete the Early Termination (ET) study procedures and observations at the time of withdrawal.

For patients withdrawn for reasons other than withdrawal of consent every effort should be made to complete the ET study procedures and observations at the time of withdrawal.

Patients who are withdrawn or discontinued from the study will not be replaced.

### **3.10. Missing, Unused, and Spurious Data**

#### **3.10.1. Efficacy Data**

Missing data for the primary efficacy endpoint will be handled by a multiple imputation model that contains the following variables: baseline fasting Lp(a) value, fasting post-baseline Lp(a) values, stratified by treatment ([Schafer 1997](#); [Schafer 1999](#)). Imputation of missing data will be conducted under a working assumption of missing at random (MAR), meaning that the propensity for a data point to be missing is not related to the missing data, but it is related to some of the observed data.

The imputations will be performed for post-baseline visits. The Markov Chain Monte Carlo (MCMC) method will be used under the multivariate normality assumption to impute the missing primary endpoint by treatment group (ISIS 681257 treatment group or pooled placebo treatment group as defined in [Section 4](#)). In order to be compliant with the normality assumption, baseline and post-baseline Lp(a) data will be log-transformed prior to the imputation process, and will be reverted back when creating the imputed dataset. Jeffreys' prior will be used to derive the posterior distribution of the parameters. The MCMC method will impute 100 datasets in order to estimate the treatment effect, where the median value across the imputed datasets will be used for patients with missing endpoint.

Missing data for the secondary endpoints will be handled similarly.

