#### **4.3.1. Analysis of the Primary Efficacy Endpoint**

As described in Section 1.2.5, the primary efficacy endpoint is the percent change in fasting Lp(a) from baseline at the primary analysis time point (Week 25 for patients in Cohorts A-C; Week 27 for patients in Cohorts D-E) achieved by ISIS 681257 compared to placebo.

The percent change from baseline in Lp(a) will be analyzed using an ANCOVA model with treatment group as factors and log-transformed baseline Lp(a) as covariate. The ANCOVA model will use  $\log(Y/X)$  as dependent variable, where Y is the post-baseline value of Lp(a) and X is the baseline value of Lp(a). The model will provide an estimate of the log ratio, which will then be converted back to the original ratio scale. The percent change from baseline will then be estimated based on the estimated ratio. Patients with missing primary endpoint will have their fasting Lp(a) value imputed using the multiple imputation method described in Section 3.10.1.

The primary endpoint will be compared between ISIS 681257 treatment groups and the pooled placebo group for each of the 100 imputed datasets. The estimates from the 100 fitted models will be combined to provide an overall estimate, with corresponding CIs and p-value (Little and Rubin, 2002). Results from the ANCOVA model will be tabulated by ISIS 681257 treatment groups compared to the pooled placebo group.

Mean (SD) percent change over time in fasting Lp(a) will be plotted by ISIS 681257 treatment group and pooled placebo group, until there are fewer than 10% of the FAS/PPS population at a given visit. Waterfall plots of by-patient percent changes from baseline to the primary analysis time point will also be provided.

The primary efficacy analysis will take place after the last patient has completed the primary analysis time point, and the database has been locked.

All primary efficacy data will be provided in data listings.

The primary efficacy analysis will be done using the FAS population.

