##### **4.3.1.1. Sensitivity Analyses of the Primary Efficacy Endpoint**

The following sensitivity analyses are planned to show the robustness of the primary analysis:

- 1) The primary analysis will be repeated using the PPS population (using an ANCOVA model and the same MCMC multiple imputation method).

- 2) The primary efficacy endpoint will be analyzed using a non-parametric Wilcoxon Rank Sum test using both the FAS and the PPS. Missing data will be handled using the same MCMC multiple imputation method as the primary analysis. The treatment effect will be estimated using the Hodges-Lehmann estimator of the location shift between ISIS 681257 treatment groups and the pooled placebo group. Asymptotic 95% CI and corresponding p-value will be provided.
- 3) The primary analysis will be repeated on the set of patients with non-missing Lp(a) values at the primary analysis time point using the FAS and the PPS.
- 4) Using controlled imputations (pattern mixture models [PMM] with ANCOVA) will be conducted to assess the robustness of the missing at random assumption. With this approach, missing not at random (MNAR) is assumed, and the mean function for the missing data from patients treated with ISIS 651257 who discontinue the study is pre-specified. Missing Lp(a) for placebo patients will be imputed using the same MCMC multiple imputation method as the primary analysis. Patients treated with ISIS 681257 who discontinue the study due to AE or lack of efficacy will have their post-discontinuation Lp(a) values imputed using estimates from the placebo patients using the copy increment from reference (CIR) approach, detailed in ([Carpenter et al. 2013](#)). The assumption is based on the fact that when a patient discontinues treatment due to informative missing data, at the time of discontinuation they would progress in a similar manner as placebo-treated patients. Otherwise, non-informative missing data will be imputed using the same MCMC method as the primary analysis, since it is assumed that those patients would have continued in a similar manner to similar patients in their own treatment group who remained on the study. Therefore, the missing data for these patients is expected to be missing at random.

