#### 4.3.2.3. Percent Change from Baseline in Other Lipid Parameters

The percent change from baseline at the primary analysis time point in fasting apoB, OxPL-apo(a), and OxPL-apoB will be compared between each ISIS 681257 treatment groups and the pooled placebo group using an ANCOVA model with treatment groups as factors and the respective log-transformed baseline lipid parameter values as covariate. Similar to the primary endpoint, the ANCOVA model will use  $\log(Y/X)$  as dependent variable, where Y and X are the post-baseline values and the baseline value of the lipid parameter being analyzed, respectively. Corresponding 95% CIs and p-value will be provided.

Mean (SD) percent change over time, until there are fewer than 10% of the FAS/PPS population at a given visit, in these fasting lipid parameters will be plotted by ISIS 681257 treatment group and pooled placebo group. Waterfall plots of by-patient percent changes from baseline to the primary analysis time point will also be provided.

All analyses of secondary endpoints will be performed using the FAS as primary and the PPS as supportive. Patients with missing data for any secondary endpoints will have their respective parameter values (LDL-C, Lp(a), apoB, OxPL-apo(a), and OxPL-apoB) imputed using the imputation method described in [Section 3.10.1](#).

All secondary endpoint data will be provided in data listings.

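### The SAP gives two conflicting rules for using the 100 imputations: a per-patient median (Section 3.10.1) and pooling of 100 fitted models (Section 4.3.1). The secondary endpoints are the most exposed.

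*SAP*

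**What the plan says.** Section 3.10.1 sets out MCMC imputation on the log scale, done separately by treatment group. It gives the purpose as "The MCMC method will impute 100 datasets in order to estimate the treatment effect" and continues, in the same sentence, "where the median value across the imputed datasets will be used for patients with missing endpoint". It then adds "Missing data for the secondary endpoints will be handled similarly".

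Section 4.3.1 compares the groups "for each of the 100 imputed datasets" and goes on: "The estimates from the 100 fitted models will be combined to provide an overall estimate, with corresponding CIs and p-value". It also says that missing Lp(a) values are "imputed using the multiple imputation method described in Section 3.10.1", so the primary analysis draws on both sections.

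For the secondary endpoints, Section 4.3.2.3 begins "Patients with missing data for any secondary endpoints will have their respective parameter values" and refers to Section 3.10.1 for the imputation. Sections 4.3.2.1 to 4.3.2.3 do not mention fitting or pooling 100 models. For the Wilcoxon and Hodges-Lehmann analysis, Section 4.3.1.1 says "Missing data will be handled using the same MCMC multiple imputation method as the primary analysis". It asks for one asymptotic interval and one p-value, but does not say how results from 100 datasets become one.

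**The concern.** The two rules cannot both hold. If every missing value is set to its median over the 100 draws, all completed datasets are identical, the between-imputation variance is zero and there is nothing to pool.

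The median rule is also unsuitable for inference. The median of draws from the predictive distribution sits close to its centre. On the log scale used by the ANCOVA, this is nearly the conditional mean. The filled-in values therefore carry no residual scatter, and the model counts them as observed. Both effects lower the reported standard error.

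For the responder endpoints, the rule turns a predicted probability into a certain 0 or 1. A patient with a 60% predicted chance of reaching the threshold becomes a definite responder, which can bias the proportion as well as its standard error.

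At stake is whether two programmers working from the same SAP would report the same intervals and p-values. A choice between the rules made after unblinding would not be prespecified.

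**Working it through.** **Inputs from the SAP.** There are 45 active patients per cohort and 54 − 45 = 9 placebo patients per cohort, so 5 × 9 = 45 pooled placebo patients (Section 3.1). The assumed SD is 20 and the assumed difference 20 points (Section 3.1). Tests are two-sided at 5% (Section 3.2).

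**Inputs assumed.** The SAP gives neither the fraction missing, m, nor the correlation, ρ, between earlier values and the endpoint. I used m = 5–20% and ρ = 0.5–0.9, with missingness at random and equal rates in both arms.

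**The plan's own figure.** For 23 against 23, a difference of 20 and SD 20, the exact two-sample t-test has 91.2% power. This agrees with the stated figure of about 90%. The point does not depend on it.

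**Formula.** For an arm mean, in units of σ²/n:
- variance reported under the median rule: (1 − m) + mρ²
- true variance: (1 − ρ²)/(1 − m) + ρ²
- SE ratio = √(reported/true); type I error = 2[1 − Φ(1.96 × ratio)]

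Example with m = 20%, ρ = 0.5: reported = 0.80 + 0.20 × 0.25 = 0.85; true = 0.75/0.80 + 0.25 = 1.1875; ratio = √(0.85/1.1875) = 0.846; type I error = 9.7%.

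| m | ρ | SE ratio | Type I error |
|---|---|---|---|
| 5% | 0.9 | 0.99 | 5.2% |
| 5% | 0.5 | 0.96 | 5.9% |
| 10% | 0.9 | 0.98 | 5.5% |
| 10% | 0.5 | 0.92 | 7.0% |
| 20% | 0.7 | 0.89 | 8.0% |
| 20% | 0.5 | 0.85 | 9.7% |

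**Simulation check.** The settings were 45 against 45, no true effect, within-arm normal imputation, 100 imputations and 6,000 replicates per setting. The table shows the reported SE under the median rule as a share of the true sampling SD, with type I error in brackets.

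| m | ρ = 0.5 | ρ = 0.8 |
|---|---|---|
| 5% | 0.96 (6.0%) | 0.98 (5.2%) |
| 10% | 0.92 (7.3%) | 0.96 (6.3%) |
| 15% | 0.88 (8.1%) | 0.94 (5.9%) |
| 20% | 0.84 (10.0%) | 0.91 (7.5%) |

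With ρ = 0, where earlier values predict nothing, the shortfall reaches 0.79 (11.9%) at 20% missing. Pooling by Rubin's rules gave 0.99 to 1.01 of the true SD and type I error of 4.4% to 5.2% in all 12 settings (m = 5–20%; ρ = 0, 0.5 and 0.8). The point estimates had nearly the same sampling SD under both rules, so the fault lies in the reported precision.

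**Effect on the primary conclusion.** With complete data the SE is 20 × √(2/45) = 4.22. At m = 20%, ρ = 0.5:
- correct SE = 4.22 × √1.1875 = 4.59; z = 20/4.59 = 4.4; 95% half-width = 9.0 points
- median-rule SE = 4.22 × √0.85 = 3.89; z = 20/3.89 = 5.1; 95% half-width = 7.6 points

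The interval is too narrow, but the conclusion is the same. This uses the SAP's percent-change SD, whereas the model works on log ratios, so it is an indication of size only.

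**The case against.** The best defence is that the primary analysis already has an explicit and valid inferential rule. Section 4.3.1 fits 100 models, combines them and cites a multiple-imputation source. It can be read as using Section 3.10.1 only for how values are imputed. A specific section normally prevails over a general one, and then the primary standard errors are sound. That stands. A reader might infer that the primary standard errors will be too small; the SAP does not support this, because the shortfall arises only if the median clause is used for inference.

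A reader might also infer that the median is the only stated rule for the Wilcoxon analysis, or that every sensitivity analysis is affected. Neither follows. Section 4.3.1.1 ties the Wilcoxon analysis to the primary analysis's method; what is missing is a way to combine its results. Sensitivity analysis 1 repeats the primary analysis. Sensitivity analysis 3 uses only patients with observed Lp(a). The MMRM of Section 4.3.3 is specified without imputation, and the added subgroup tables are expressly not imputed.

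For the secondary endpoints, handling them similarly to the primary could be taken to bring in its pooling. That is possible, but Section 3.10.1 is the only place cited, and the median clause is the only explicit instruction there on how the 100 datasets are used.

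The defence that the median is meant only for plots or listings has no support in the text. The clause is attached to estimating the treatment effect, and the later supplement on subgroups and compliance leaves it unchanged.

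**Conclusion.** The clause is wrong as written and should be corrected. Sections 3.10.1 and 4.3.1 give incompatible rules for the primary analysis, and following Section 4.3.1 resolves the conflict validly. The exposure is greatest for the secondary ANCOVAs and the responder logistic models, which cite only Section 3.10.1.

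The size is conditional. Over m = 5–20% and ρ = 0.5–0.9, using the median for inference would understate standard errors by 1–2% at the favourable end and about 16% at the other, with type I error of about 5% to 10%. With few missing values and well-predicted endpoints the effect is negligible. Under the SAP's assumed effect a reversed primary conclusion is unlikely; the harm is overstated precision and an ambiguous prespecification. Section 3.7 sets no multiplicity procedure, so nothing elsewhere in the plan would absorb any inflation.

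**What to change.** - **Section 3.10.1:** delete the median clause, or restrict it to by-patient displays such as the waterfall plots.
- **Primary and secondary ANCOVAs, responder models:** state that each is run in every one of the 100 imputed datasets and combined by Rubin's rules. Derive responder status within each dataset from the imputed Lp(a).
- **Sparse responders:** prespecify a fallback, for example penalised logistic regression. Entry requires Lp(a) of at least 60 mg/dL, the assumed placebo reduction is 10%, and one threshold is 30 mg/dL. Placebo may therefore have few or no responders, and ordinary logistic models could separate in individual datasets.
- **Wilcoxon analysis:** pool the Hodges-Lehmann estimates with their asymptotic standard errors by Rubin's rules and take the interval and p-value from the pooled result. Alternatively, pool the standardised rank statistic. State which.

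The cost is a short SAP revision, a little more programming, and slightly wider intervals wherever the median would otherwise have been used. No data collection changes.

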#### **3.10.2. Adverse Event Data**

When tabulating AE data, partial start dates will be handled as follows:

- If the year, month, and day are all missing, then set the onset day to the date of the first dose.

- If the month and day are missing, and the year is:
  - the same as the year of first dose, then set the onset day as the first day of the month of the first dose;
  - earlier than the year of first dose, then set the onset day as December 31;
  - after the year of the first dose, then set the onset day as January 1.
- If only the day is missing, then
  - if the month/year is the same as the first dose, then set the onset day as the date of first dose;
  - if the month/year is earlier than the month/year of the first dose, then set the onset day as the last day of the month;
  - if the month/year is later than the month/year of the first dose, then set the onset day as the first day of the month.

Partial end dates will only be imputed if the year is non-missing:

- If the month and day are missing, and the year is the same as the year of the last dose then set the end day as the last day of the month of the first dose. Otherwise, set the end date as December 31.
- If only the day is missing, then set the end day as the last day of the month.

If the imputed start date is later than the imputed end date then set the imputed start date to the imputed end date.

### 3.10.3. Prior and Concomitant Medication Data

When tabulating prior/concomitant medication data, partial start dates will be handled as follows:

- If the year, month, and day are all missing, then set the start date to the date of first dose.
- If the month and day are missing and the year is earlier than the year of the first dose, then set the start date to December 31. Otherwise, set the start date to January 1.
- If only the day is missing, if the month/year is earlier than the month/year of the first dose then set the start date to the first day of the month. Otherwise, set the start date to the last day of the month.

Partial end dates will only be imputed if the year is non-missing:

- If the month and day are missing then set the end date to December 31.
- If only the day is missing, then set the end day as the last day of the month.

If the imputed start date is later than the imputed end date then set the imputed start date to the imputed end date.

### **3.11. Visit Windows**

It is expected that all visits should occur according to the protocol schedule within the allowed protocol-specified window. All data will be tabulated per the evaluation visit as recorded on the eCRF even if the assessment is outside of the visit window. In data listings, the relative day of all dates will be presented.

### **3.12. Interim Analyses**

No interim analyses are planned for this study.

## **4. STUDY ANALYSES**

Treatment groups are ISIS 681257 treatment groups and pooled placebo group. ISIS 681257 treatment groups include:

ISIS 681257 20 mg (Every 4 weeks)

ISIS 681257 40 mg (Every 4 weeks)

ISIS 681257 60 mg (Every 4 weeks)

ISIS 681257 20 mg (Every 2 weeks)

ISIS 681257 20 mg (Every week)

Within cohort comparisons between patients receiving ISIS 681257 and patients receiving placebo will be performed for selected safety endpoints, as appropriate.

### **4.1. Patient Disposition**

Patient disposition will be tabulated by ISIS 681257 treatment group and pooled placebo group. Tabulations will include the number screened, the number randomized, the number treated in total, the number in each patient population for analysis, the number who completed treatment, the number who withdrew prior to completing treatment and reason(s) for withdrawal, the number of patients who discontinued prior to completing post-treatment follow-up, along with reasons for ET post-treatment.

A by-patient data listing of study completion information including the reason for premature study withdrawal, if applicable, will be presented.

### **4.2. Demographics and Baseline Characteristics**

Demographics and baseline characteristics will be summarized and presented by ISIS 681257 treatment group and pooled placebo group. Age (years), height (cm), weight (kg), race, gender, ethnicity and body mass index (BMI, kg/m^2), as well as fasting lipids results including Lp(a), apoB, LDL-C, OxPL-apo(a), and OxPL-apoB will be summarized using descriptive statistics. Demographic and baseline data for each patient will be provided in data listings.

Medical history will be coded using MedDRA v20.0 and presented by system organ class and preferred term by ISIS 681257 treatment groups and pooled placebo group. If a patient had more than one medical history event within a system organ class, the patient is counted once for each preferred term and once for the system organ class. Medical history data will also be provided in by-patient listings.

Cardiovascular disease history data will be tabulated by ISIS 681257 treatment group and pooled placebo group. A by-patient data listing will also be provided.

Ancillary procedures and genetic testing data will be provided in by-patient listings.

Demographics and baseline characteristics summary tabulations will be produced for the Safety Set, the FAS, and the PPS.

### **4.3. Efficacy Evaluation**

All efficacy analyses related to Lp(a) will be primarily performed, and the actual changes in Lp(a) will be presented in nanomoles per liter (nmol/L) because the direct output of the Lp(a) assay used in this study is provided in molar units. Due to high degree of size heterogeneity of apo(a) protein, use of molar concentrations is considered highly preferable over use of mass concentrations (mg/dL) (Markovina SM and Albers JJ, 2016). For completeness, the actual Lp(a) results will also be presented in mg/dL using conversion factor of 2.5. Although the conversion factor for transforming Lp(a) values from nmol/L to mg/dL highly varies due to variability of mass of nonprotein components of Lp(a), it is accepted in the literature that Lp(a) in nmol/L is approximately 2.4-2.5 fold higher than Lp(a) in mg/dL (Tsimikas S et al 2015, Viney et al, 2016).

#### **4.3.1. Analysis of the Primary Efficacy Endpoint**

As described in Section 1.2.5, the primary efficacy endpoint is the percent change in fasting Lp(a) from baseline at the primary analysis time point (Week 25 for patients in Cohorts A-C; Week 27 for patients in Cohorts D-E) achieved by ISIS 681257 compared to placebo.

The percent change from baseline in Lp(a) will be analyzed using an ANCOVA model with treatment group as factors and log-transformed baseline Lp(a) as covariate. The ANCOVA model will use  $\log(Y/X)$  as dependent variable, where Y is the post-baseline value of Lp(a) and X is the baseline value of Lp(a). The model will provide an estimate of the log ratio, which will then be converted back to the original ratio scale. The percent change from baseline will then be estimated based on the estimated ratio. Patients with missing primary endpoint will have their fasting Lp(a) value imputed using the multiple imputation method described in Section 3.10.1.

The primary endpoint will be compared between ISIS 681257 treatment groups and the pooled placebo group for each of the 100 imputed datasets. The estimates from the 100 fitted models will be combined to provide an overall estimate, with corresponding CIs and p-value (Little and Rubin, 2002). Results from the ANCOVA model will be tabulated by ISIS 681257 treatment groups compared to the pooled placebo group.

Mean (SD) percent change over time in fasting Lp(a) will be plotted by ISIS 681257 treatment group and pooled placebo group, until there are fewer than 10% of the FAS/PPS population at a given visit. Waterfall plots of by-patient percent changes from baseline to the primary analysis time point will also be provided.

The primary efficacy analysis will take place after the last patient has completed the primary analysis time point, and the database has been locked.

All primary efficacy data will be provided in data listings.

The primary efficacy analysis will be done using the FAS population.

